The attached flow chart illustrates the study design (Figure 1). After identification and trial entry, we will complete intake questionnaire to determine what type of vestibular migraine category the patients qualify for, a standard of care office visit with history and physical (Standard of Care) to review symptoms and previous treatment, patients height and weight (standard of care) will be obtained. Patients will complete a standard of care audiology assessment, and the following questionnaires: MSQ (Migraine Symptom Questionnaire) Version 2.1, DHI (Dizziness Questionnaire) , C-SSRS (Columbia Suicide Severity Rating Scale) and the MoSQ (Motion Sensitivity Questionnaire). All drug naive patients will undergo a one month lead in of treatment involving dietary and behavioral control of migraine. Emphasis will be given to cessation of known migraine triggers such as caffeine, sodas, chocolates, alcohol (especially red wine) and aged cheeses. Patients who have complete control of their symptoms with diet and behavior modification alone will be followed for a total of 4 months to determine the durability of symptom relief. Patients who fail behavior modification during the 2 to 4 month time point can chose to enter the drug treatment portion of the study, as defined below.

At the one month point, patients will be brought into the clinic for a office visit or contacted by phone and will complete medical history, MSQ V2.1, DHI, C-SSRS and the MoSQ, then will be randomization to either nortriptyline or topiramate will occur. Randomization will occur by opening the lowest numbered of a stack of envelopes which will contain a randomly preselected

Protocol Title:

A Prospective randomized cross-over trial of nortriptyline and topiramate in the initial treatment of vestibular migraine

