opening the lowest numbered of a stack of envelopes which will contain a randomly preselected card indicating which drug is to be used. The nortriptyline will be given in an escalating fashion, starting at 25 mg PO qhs for 2 weeks, followed by 50 mg PO qhs for 2 weeks, and finally 75 mg PO qhs. Patients will be encouraged to use the lowest effective dose and to self-titrate their medication. Topiramate dosing will be 25 mg PO qhs for 1 week, followed by 25 mg BID for 1 week, followed by 25 mg in the morning and 50 mg qhs for 1 week, and finally 50 mg BID. Patients will be allowed considerable leeway in adjusting their dosage and will be encouraged to stay on the lowest effective dose. Medication will be provided open label to the patient and paid for through the patients' insurance, as this intervention falls within current standard practice, and is not investigational.

After two, three and four months on drug patients will be brought into the clinic for a office visit or contacted by phone with history, and will complete MSQ V2.1, DHI, C-SSRS and the MoSQ, then patients will be offered the opportunity to switch to the other drug. Those patients who wish to switch drugs will first be weaned off their current drug over a one week time period. Patients who elect to stay on their initial drug will be followed for a total of four months. Patients who opt for trial of a second drug will then be started on the second drug via a self-titrating protocol as described above and followed on that drug for up to 4 months.

Our clinical experience has shown that on occasion patients will refuse to take more than a few doses of nortriptyline or topiramate due to intolerable side effects. Such patients will be allowed to immediately initiate therapy with the other drug. The medication change can be done with a phone call to their pharmacy without an office visit, as is done in standard of care. Also, patients who already follow a rigorous migraine diet will be allowed to enter the drug treatment phase immediately. In our experience, such patient make up less than 5% of the population that presents for treatment of vestibular migraine.

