Due to known drug interactions, patients taking the following medications will be excluded. Nortriptyline: monoamine oxidase inhibitors (MAO) such as phenelzine. Patients on oral contraceptives will be asked to use a secondary method as nortriptyline can reduce the effectiveness of oral contraceptives.

Topiramate: acetazolamide (kidney stones), digoxin

An electronic health record (EPIC) will be used for secure collection of all patient data. Questionnaires filled out by patients will be scanned into EPIC.

A sample size of 100, which nets 90 subjects into the randomized medication trial (two equal groups of 45 subjects each), yields a power of 82% to detect a difference in patient-reported effectiveness/acceptability between the nortriptyline and topiramate groups after two months of medication use. This sample size estimate assumes 60% of subjects using nortriptyline report it as effective/acceptable, in contrast to half as many subjects (or 30%) using topiramate. The power calculation is based on a two-sized Z-test with pooled variance and targeted significance level (alpha) of 0.05. The expected difference in outcome between the two groups is based on our prior research ([name], 2012).

Adverse effects of the two drugs will be assessed. Specifically, the following known side effects will be asked about and recorded.

Nortriptyline: somnolence, weight gain, dry mouth, blurred vision

Topiramate: Weight loss, parasthesias, forgetfulness, nausea, diarrhea, fatigue

The subjects will be allowed to maintain therapy or taper off the drugs. It is anticipated that those that derive benefit from the drugs will choose to stay on them. All patients will have the option of remaining under our care outside of the study.

c) If the proposed study is a clinical trial where a drug, vaccine, device or other treatment is compared to a placebo group or comparison treatment group, what are the guidelines or endpoints by which early decisions regarding efficacy or lack of efficacy can be made? For example, it may be reasonable to stop enrollment on a study when efficacy has already been clearly demonstrated, to avoid unnecessary enrollments of additional subjects. Alternatively, it may be reasonable to stop enrollment when it is clear that efficacy will never be demonstrated, given the statistical power of the study as designed. Describe the guidelines that are in place to assist in making these determinations, if relevant to the proposed study.

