Our clinical experience has shown that on occasion patients will refuse to take more than a few doses of nortriptyline or topiramate due to intolerable side effects. Such patients will be allowed to immediately initiate therapy with the other drug. Otherwise the physician will be in close contact with the patients and if there are any concerns or problems patients will be given the option to stop or switch treatment methods and if the PI feels necessary will recommend alternative treatment.

d) Describe how data analysis will be performed (statistical tests, methods of evaluating data) and indicate the smallest group/unit for which separate reporting will occur. For studies involving a questionnaire, if data and reliability information are available, please describe or provide

Protocol Title: A Prospective randomized cross-over trial of nortriptyline and topiramate in the initial treatment of vestibular migraine

references. For full board, unfunded studies describe sample size determination and power analysis. If none, please justify.

The core of the analysis plan includes two components: (1) nortriptyline versus topiramate comparison at two-months and (2) cross-over. In addition to measuring differences in patient-reported effectiveness/acceptability between nortriptyline versus topiramate for the first component, repeated measures ANOVA will be employed to assess change in Migraine Specific Quality of Life (MSQ) and Dizziness Handicap Inventory (DHI) between the groups. A subgroup analysis for the three subtypes of vestibular migraine will be also conducted. Descriptive statistics for subject attributes will be reported by group and assessed for potential confounding. In the second component, data from subjects who choose to try the alternate medication will be used for the cross-over analysis. This plan calls for comparing change in each subject's DHI score for their experience using nortriptyline versus topiramate. With this approach each subject serves as its own control, which helps to minimize selection bias in this component of the study. Significance will be set at the alpha level of 0.05 for both components of the analysis plan. All analyses will be coordinated by [name] and staff at the Saint Louis University Center for Outcomes Research, an academic unit that specializes in statistical analysis for clinical studies.

Please save frequently

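### MSQ and DHI change is compared between the drugs without adjusting for the pre-randomisation score; adding that covariate is a precision gain at almost no cost, not the repair of an error.

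*Combined protocol and SAP*

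**What the plan says.** The first component of the analysis in section 3d is the "nortriptyline versus topiramate comparison at two-months". Its headline outcome is patient-reported effectiveness/acceptability. In addition, "repeated measures ANOVA will be employed to assess change in Migraine Specific Quality of Life (MSQ) and Dizziness Handicap Inventory (DHI) between the groups". No covariate is named. The nearest text is "Descriptive statistics for subject attributes will be reported by group and assessed for potential confounding".

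Under section 3b, MSQ and DHI are completed at study entry and again after the one-month diet lead-in, when patients "will complete medical history, MSQ V2.1, DHI, C-SSRS and the MoSQ, then will be randomization". Two routes depart from this pattern:

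- Early entry: "patients who already follow a rigorous migraine diet will be allowed to enter the drug treatment phase immediately". The protocol puts these patients at under 5% of those presenting.
- Late entry: "Patients who fail behavior modification during the 2 to 4 month time point can chose to enter the drug treatment portion of the study".

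After the on-drug questionnaires, "then patients will be offered the opportunity to switch to the other drug". Sections 2a, 3b and 3c also allow an earlier switch for intolerance.

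The sample size paragraph of 3b plans 90 randomised patients, 45 per drug, which "yields a power of 82% to detect a difference in patient-reported effectiveness/acceptability". No SD, correlation, target difference or power is given for MSQ or DHI.

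**The concern.** If baseline is one of two time levels, the group-by-time test of a repeated measures ANOVA is the two-sample comparison of change scores. That comparison subtracts the baseline score with its slope fixed at 1. ANCOVA estimates the slope from the data and so removes at least as much residual variance in large samples. The covariate is already in the visit schedule, so the gain needs no extra patients or visits.

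The precision of the two-month MSQ and DHI comparisons is what is at stake. Sections 1a and 2a name these questionnaires among the measures of response, and the plan makes no power statement for them.

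There is also a gap in specification. Most patients have two candidate baselines, intake and post-diet, and 3d does not say which one change is measured from. In an open-label trial that choice should be fixed before the data are seen.

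**Working it through.** **1. The plan's own figure.** Inputs from 3b: 60% v 30%, 45 per arm, two-sided alpha 0.05, Z-test with pooled variance.

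- Pooled proportion: 0.45.
- Null SE: √(2 × 0.45 × 0.55 / 45) = 0.1049.
- SE under the alternative: √((0.6 × 0.4 + 0.3 × 0.7) / 45) = 0.100.
- Power: Φ((0.30 − 1.96 × 0.1049) / 0.100) = Φ(0.944) = 82.8%.

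Exact enumeration of the same test gives 81.8%. The stated 82% is reproduced. It belongs to the binary outcome, so nothing below changes it.

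**2. Change v baseline-adjusted, equal SDs.** Assumptions, none of them in the documents: one baseline and one follow-up score, both with SD 1, and correlation r.

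- Variance per patient, change: 2(1 − r).
- Variance per patient, adjusted: 1 − r².
- Ratio: 2/(1 + r).
- Slope-estimation cost with 90 patients: factor 1 + 1/(90 − 4) = 1.0116. The net ratio is the ratio divided by this factor.

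| r | Change | Adjusted | Ratio | Net ratio |
|---|---|---|---|---|
| 0.3 | 1.40 | 0.91 | 1.54 | 1.52 |
| 0.5 | 1.00 | 0.75 | 1.33 | 1.32 |
| 0.7 | 0.60 | 0.51 | 1.18 | 1.16 |
| 0.8 | 0.40 | 0.36 | 1.11 | 1.10 |
| 0.9 | 0.20 | 0.19 | 1.05 | 1.04 |

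A simulation of 20,000 trials with 45 per arm gave ratios of 1.53, 1.32, 1.16, 1.09 and 1.04. Type I error was 4.8% to 5.2% for both methods, so both are valid.

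**3. Unequal SDs.** Let k be the baseline SD divided by the follow-up SD, with follow-up SD 1. Change variance is 1 + k² − 2rk and adjusted variance is still 1 − r².

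| r | k = 0.8 | k = 1.0 | k = 1.2 |
|---|---|---|---|
| 0.3 | 1.27 | 1.54 | 1.89 |
| 0.5 | 1.12 | 1.33 | 1.65 |
| 0.7 | 1.02 | 1.18 | 1.49 |
| 0.8 | 1.00 | 1.11 | 1.44 |
| 0.9 | 1.05 | 1.05 | 1.47 |

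For example, at r = 0.7 and k = 0.8 the ratio is (1 + 0.64 − 1.12)/0.51 = 0.52/0.51 = 1.02. The ratio is exactly 1 when r = k, because a slope of 1 is then the best slope. In that case adjustment gains nothing and costs the 1% for estimating the slope.

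**4. Mean of intake and post-diet scores as baseline.** With equal SDs and the same r between every pair of scores, change variance is 1.5(1 − r) and adjusted variance is 1 − 2r²/(1 + r). The ratios are 1.22, 1.125, 1.06, 1.04 and 1.02 at r = 0.3, 0.5, 0.7, 0.8 and 0.9.

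**5. What this means for power.** Illustration only: an assumed difference of 0.5 SD, 45 per arm, equal SDs, two-sided t-test at 0.05, with the slope cost included.

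| r | One baseline: change v adjusted | Mean of two: change v adjusted |
|---|---|---|
| 0.3 | 51% v 69% | 63% v 71% |
| 0.5 | 65% v 77% | 77% v 81% |
| 0.7 | 86% v 90% | 94% v 95% |
| 0.8 | 96% v 97% | 99% v 99% |
| 0.9 | >99% v >99% | >99% v >99% |

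**The case against.** The strongest reply is that nothing here is broken. Change from baseline already uses the baseline score, randomisation makes the comparison unbiased, and the outcome that sets the sample size is binary. All of that stands, and it is why the point is an improvement and not a correction.

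A second reply is that the gain may be negligible. That also stands. The documents give neither r nor the SDs, and for some plausible pairs (r = 0.8 with k = 0.8) the ratio is 1.00. The ANOVA description does not say which visits enter or whether baseline is a time level, so the two-score calculation is one reading of it. The flow chart and grant application are listed as attachments but are not reproduced, and they might say more.

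A third reply is that the statement on confounding covers adjustment. It does not. It promises description and assessment of subject attributes, without naming a covariate or a model.

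For patients who enter the drug phase late, 3b does not explicitly schedule questionnaires at that entry; only its general reference to monthly visits might cover them. Their last score before randomisation could therefore be some weeks old. This weakens the covariate for those patients, but it does not bias the randomised comparison.

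A reader might go further and infer that the MSQ and DHI comparison is biased, or that the 82% power is overstated. The documents support neither. Both methods hold their type I error, and the 82% reproduces for a different outcome.

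**Conclusion.** The point holds as a free improvement. Section 3d leaves out a covariate that the trial already collects. Including it is never less precise in large samples, and its cost at 90 patients is about 1% of variance.

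The gain cannot be fixed from the documents. With equal SDs, change-score variance is 1.54 to 1.05 times the adjusted variance over correlations of 0.3 to 0.9. With baseline SD between 0.8 and 1.2 times follow-up SD, the range is about 1.0 to 1.9. With the two pre-randomisation scores averaged and equal SDs, it is 1.22 to 1.02.

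It is tempting to read the equal-SD table as a rule that the gain is material up to a correlation of about 0.7 and minor above 0.8. That does not carry over to unequal SDs: at r = 0.7 the ratio is 1.02 for k = 0.8 and 1.49 for k = 1.2, and the documents support no particular k.

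**What to change.** In section 3d, replace the repeated measures ANOVA sentence with:

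> The two-month DHI (and, separately, MSQ) score will be compared between the drugs as randomised, including patients who switched drug before two months, by a linear model (ANCOVA) with the last score of the same questionnaire before randomisation as covariate (the post-diet score, or the intake score for patients who skip the lead-in).

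This names the baseline, the time point and the analysis groups. It needs no change to sample size, visits or treatment.

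One matter should be reconciled separately. Section 3b lists on-drug questionnaires after two, three and four months, but later describes assessment at monthly visits, so it is unclear whether a month-1 on-drug score exists. The proposed sentence does not depend on the answer.

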The response to therapy will be assessed during monthly visits with the use of the MSQ, DHI and MoSQ questionnaires. Patients will be provided compensation for participating in the study. \$60 dollars will be paid to each patient for each month that they participate in the study. Our goal is to recruit 100 patients over the span of one year.

Data which will be collected include age, sex, height, weight, body mass index (BMI), prior head MRI or CT, results of vestibular testing, family history of migraine. A careful history will focus on vestibular migraine comorbidities such as visual scotoma, ability to ride in the back seat of a car, and history of "sinus pain".

Patients will be identified as having one of three subtypes of vestibular migraine, based on their symptoms and history as obtained during their initial visit.

Criteria for Neuhauser definite vestibular migraine (dVM): (Neuhauser, 2009):

1. Episodic vestibular symptoms of at least moderate severity.
2. Current or previous history of migraine according to the 2004 criteria of the International Headache Society (IHS)
3. One of the following migrainous symptoms during 2 or more attacks of vertigo: migrainous headache, photophobia, phonophobia, visual aura, or other aura
4. Other causes ruled out by appropriate investigations

Criteria for probable vestibular migraine (pVM):

1. Episodic vestibular symptoms of at least moderate severity
2. One of the following
 - A. current or previous history of migraine according to the 2004 criteria of the IHS
 - B. migrainous symptoms during vestibular symptoms
 - C. migraine precipitants of vertigo in > 50% of attacks: food triggers, sleep irregularities, or hormonal change
 - D. Response to migraine medications in more than 50% of attacks
3. Other causes ruled out by appropriate investigations

Protocol Title:

A Prospective randomized cross-over trial of nortriptyline and topiramate in the initial treatment of vestibular migraine

Criteria for (non-Neuhauser vestibular migraine or nNVM) will include those patients who do not fit the criteria for dVM and pVM but are felt by the investigator to have underlying migraine as a possible cause of their dizziness. This includes patients with a remote history of migraines, those with visual auras without headache, those with recurring self-described "sinus pain" and those with significant motion intolerance, either to their own head motion or motion in their surroundings.

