5. Describe any risks related to performing study procedures. Please include all investigational, non-

Protocol Title: A Prospective randomized cross-over trial of nortriptyline and topiramate in the initial treatment of vestibular migraine

investigational, and non-invasive procedures (e.g., surgery, blood draws, treadmill tests).

n/a

6. Describe any risks related to the use of radioisotopes/radiation-producing machines (e.g., X-rays, CT scans, fluoroscopy).

7. Describe why this investigational compound/drug/device/procedure's risks/benefits are potentially better than standard of care or other common alternatives. Any standard treatment that is being withheld must be disclosed and the information must be included in the consent form. *?HELP?*

This drug is standard of care so the risks/benefits are identical to that of standard of care.

8. Describe any psychological, social, or legal risks the subject may experience. *?HELP?*

Risk of Questionnaires:

Some questions on the questionnaires may make patients feel uncomfortable, they may not answer any question they do not feel comfortable answering

Loss of Confidentiality

Page numbers from a sponsor's protocol/grant may be referenced in 9.9 and 9.10.

9. Special Precautions. Describe the planned procedures for protecting against or minimizing potential risks. If appropriate, include the standards for termination of the participation of the individual subject. Discuss plans for ensuring necessary medical or professional intervention in the event of adverse effects to the subjects.

Patients will be closely followed while they are on study and can stop or change medications if they do not like the medications effects that they are on. You will be given the Columbia Suicide Severity Rating Scale at each appointment to evaluate any changes in mood and behavior related to suicidal thoughts. [name] will be available to evaluate and treat or refer to a specialist for any adverse reactions.

10. Reproductive Risks.

a. Please list the pregnancy category of any drugs or N/A.

D

Protocol Title: A Prospective randomized cross-over trial of nortriptyline and topiramate in the initial treatment of vestibular migraine

b. Please describe any reproductive risk associated with any part of the research study. Include any data from other studies (animal or human).

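### Repeated measures ANOVA is planned for DHI and MSQ with no visits, analysis set or missing-score rule; a mixed model on all observed scores would be safer at almost no cost

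*Combined protocol and SAP*

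**What the plan says.** Section 3d divides the analysis into two components, "1) nortriptyline versus topiramate comparison at two-months and (2) cross-over". Within the first, besides patient-reported effectiveness/acceptability, "repeated measures ANOVA will be employed to assess change in Migraine Specific Quality of Life (MSQ) and Dizziness Handicap Inventory (DHI) between the groups". That is all the plan says about this model. It gives no list of visits, covariance assumption, analysis set, rule for incomplete forms or missing-data method, and no other section supplies them.

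Section 3b describes the assessment schedule in two ways. One sentence reads "After two, three and four months on drug patients will be brought into the clinic for a office visit or contacted by phone", which names no one-month visit on drug. Another reads "The response to therapy will be assessed during monthly visits with the use of the MSQ, DHI and MoSQ questionnaires", which implies one.

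Four other statements bear on gaps in the scores:

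- Section 9.8 says of the questionnaires that patients are free to skip items: "they may not answer any question they do not feel comfortable answering".
- Section 3b lets a patient who cannot tolerate one drug start the other: "The medication change can be done with a phone call to their pharmacy without an office visit".
- Section 2a says that patients who switch early continue to be followed on the second drug.
- The sample size in 3b "assumes 60% of subjects using nortriptyline report it as effective/acceptable, in contrast to half as many subjects (or 30%) using topiramate". Its only allowance for loss, from 100 to 90, comes before randomisation.

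**The concern.** Classical repeated measures ANOVA needs a full row of data. A patient with a score at randomisation and at month 2 but none at another modelled visit is removed from that scale's analysis. With three or more visits it also assumes a restricted correlation pattern.

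Two things are at stake. One is power, because observed scores are discarded from groups of only 45. The other is the protection that randomisation gives. If patients who do poorly early are more likely to lack a later score, and this happens more on one drug, the complete cases are no longer the randomised groups. The drug that loses more poor responders then looks better than it is. Treatment is open label, patients may stop or taper off, and the plan itself expects a large difference in acceptability. Unequal loss related to response is therefore a reasonable scenario to plan for.

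**Working it through.** **The plan's own figure.** "The power calculation is based on a two-sized Z-test with pooled variance and targeted significance level (alpha) of 0.05". With p1 = 0.60, p2 = 0.30, mean 0.45 and n = 45 per arm:

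- Null SE = √(2 × 0.45 × 0.55 / 45) = 0.1049.
- Alternative SE = √((0.24 + 0.21) / 45) = 0.100.
- Power = Φ((0.30 − 1.96 × 0.1049) / 0.100) = Φ(0.944) = 82.75%.

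This agrees with the stated 82%. It applies to the binary outcome only and assumes that all 45 per arm are analysed. No power is stated for DHI or MSQ.

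**Loss of patients under complete-case analysis.** The documents give no missing rate, SD or correlation, so everything below rests on assumed inputs. If a fraction m is missing independently at each of k on-drug visits, 45 × (1 − m)^k patients per arm remain. The effect is set at 0.606 SD, the value that gives 82% power with 45 per arm.

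| On-drug visits modelled | 5% missing: n per arm, power | 10% missing | 20% missing |
|---|---|---|---|
| 1 | 42.8, 80% | 40.5, 78% | 36.0, 73% |
| 2 | 40.6, 78% | 36.5, 74% | 28.8, 63% |
| 3 | 38.6, 76% | 32.8, 69% | 23.0, 54% |

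Only part of this loss can be recovered by changing the model.

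**Like-for-like power at month 2.** Assumed: SD 20; correlations 0.5 to 0.65, with 0.5 between randomisation and month 2; true month-2 difference 12 points; scores at randomisation, month 1 and month 2; 10% missing at random at each of months 1 and 2.

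- The SD of change is √(2 × 400 × (1 − 0.5)) = 20.
- No gaps: SE = 20 × √(2/45) = 4.22, power = Φ(12/4.22 − 1.96) = 81%.
- Complete cases, 45 × 0.9² = 36.45 per arm (about 73 in all): SE = 4.68, power = Φ(2.56 − 1.96) = 73%. Simulation gives about 72%.
- Likelihood model on all observed scores: complete-case variance was 1.15 times larger in simulation, so SE = 4.68/√1.15 = 4.37 and power = Φ(2.75 − 1.96) = 78%. Simulation gives about 77%.
- Randomisation and month 2 only, 40.5 per arm: SE = 4.44, power = Φ(2.70 − 1.96) = 77% (75% in simulation). Here the complete-case variance is only about 1.03 times larger, so there is little to recover.

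**Bias with no true drug difference.** Simulated with 45 per arm and three visits; the month-2 score may be missing depending on early change.

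| Assumed loss | Complete cases | Likelihood model |
|---|---|---|
| Same process in both arms (82% complete in each) | about 0 | about 0 |
| Mild imbalance (90% v 96% complete) | 0.03 SD | 0.00 SD |
| Moderate imbalance (78% v 92% complete) | 0.08 SD | 0.00 SD |
| Strong imbalance (about 37% v 17 to 20% missing) | 2 to 5 points at SD 20 | under 0.2 points |

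At SD 20, 0.03 and 0.08 SD are 0.6 and 1.6 points. In the first three rows the two methods had nearly equal variance (ratios 0.99 to 1.01), so the benefit there is removal of bias and not extra power. In the last row the ANOVA false-positive rate was 8% when loss was tied to response in both arms and 23% when it was tied to response on topiramate only. The likelihood model gave about 5%. These rates follow from the assumed unequal loss and do not predict this trial's error rate.

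**The case against.** The strongest reply is that the plan never says patients with a gap will be dropped. That is a property of the classical method, and the same label is sometimes used for mixed models. This stands, and it is a reason to name the model. DHI and MSQ would also normally be analysed separately, so a missing DHI score need not remove a patient from the MSQ analysis.

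A reader might infer that the documents show missing scores to be likely and unequal by drug. They do not. The 60% and 30% are assumed acceptability rates at two months, not loss rates. The pharmacy call changes a prescription and cancels no assessment. Early switchers continue to be followed, so they raise a question of analysis set and not of missing scores. Skipped items are not specific to a drug. Phone contact (3b), payment of $60 per visit (8i) and close physician contact (3c) all work against loss. What remains is that unequal loss is plausible.

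A reader might also infer a large power advantage by setting the overall drug-by-time F test against a single month-2 contrast. Those are different tests, and the result depends on the assumed month-1 effect. With the gaps above, F-test power was about 69% with a month-1 effect of 6 points, but 82 to 84% with an effect of 12 or 0. The fair comparison is 72% against 77%.

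Finally, if there is no one-month score on drug and only randomisation and month 2 are modelled, the correlation assumption is met automatically and the power gain is close to nil. This also stands. It cannot be settled while the two schedule statements in 3b differ.

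**Conclusion.** The concern holds as a weakness in the choice and specification of the model, not as a demonstrated error. If the ANOVA is run in its classical form, it discards observed scores and has no protection against loss that depends on early response and differs by drug. Under the stated assumptions the recoverable power is about 5 points with an intermediate visit and about 2 points or less without one. Bias ranges from about zero (same loss process in both arms, no true difference), through 0.03 to 0.08 SD, to 2 to 5 points under strong assumed imbalance.

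The likelihood model removes this bias only when loss depends on scores that were observed. It gives no guarantee when loss depends on the unseen score. DHI and MSQ are analysed in addition to the one powered outcome, so this does not undermine the sample size calculation. The change should still be made, because the randomised comparison of these scales depends on it and the better method costs almost nothing.

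**What to change.** In 3d, replace repeated measures ANOVA with a likelihood-based mixed model for repeated measures, fitted separately for DHI and MSQ, and specify:

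- all randomised patients, analysed by assigned drug, including those who switch before month 2;
- every observed score from randomisation to month 2, with no patient removed because of a gap;
- drug, visit and drug-by-visit terms, with unstructured covariance;
- the drug difference in change from the pre-randomisation score at month 2 as the result for each scale, with later scores kept for other analyses;
- a scoring rule for forms with skipped items;
- a sensitivity analysis for loss that depends on unobserved scores, for example shifting the missing month-2 scores by a range of amounts that may differ by drug.

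Reconcile the two statements in 3b on which on-drug visits collect the questionnaires, so that the visits in the model are defined. The cost is about a paragraph of analysis text, with no new patients and no data beyond what the reconciled schedule already collects.

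### The randomised two-month comparison needs covariates fixed in advance; assessing attributes by group for confounding adds essentially nothing there

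*Combined protocol and SAP*

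**What the plan says.** Section 3d splits the analysis into a drug comparison at two months and a cross-over part built on patients who choose to change drug. Within the first part, after the subgroup analysis and before the second part begins, it states: "Descriptive statistics for subject attributes will be reported by group and assessed for potential confounding".

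The likely attributes are in section 3b: "Data which will be collected include age, sex, height, weight, body mass index (BMI), prior head MRI or CT", followed by vestibular test results and family history of migraine. That makes eight, apart from history items and the three-level subtype. Section 3b also has MSQ and DHI completed at the one-month point, before a numbered envelope assigns the drug.

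The sample size paragraph in 3b "nets 90 subjects into the randomized medication trial (two equal groups of 45 subjects each" and uses a "two-sized Z-test with pooled variance and targeted significance level (alpha) of 0.05", which has no covariates. Section 3d names a repeated measures ANOVA for MSQ and DHI, also without covariates, and adds: "Significance will be set at the alpha level of 0.05 for both components of the analysis plan". No section names an adjustment covariate, a rule for calling an attribute a confounder, an adjusted model, or which result would be primary.

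**The concern.** Allocation by envelope means that any baseline difference between arms as randomised is chance. Looking for confounders there tends to pick attributes because they differ and not because they predict outcome. A strongly prognostic attribute that happens to balance would be left out, although including it would sharpen the estimate.

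Medication is open label and the plan gives no rule, so the decision to adjust could also be taken with outcomes visible by drug. At stake are precision on MSQ and DHI and a clear statement of which result counts. The truly non-randomised comparisons, where confounding is a real threat, have no such assessment assigned to them.

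**Working it through.** **1. The plan's own figure.** Inputs from section 3b: 45 per arm, 60% against 30%, two-sided alpha 0.05, pooled variance. The mean rate is 0.45.

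- SE under the null: √(2 × 0.45 × 0.55 / 45) = 0.1049
- SE under the alternative: √((0.60 × 0.40 + 0.30 × 0.70) / 45) = 0.1000
- Power: Φ((0.30 − 1.960 × 0.1049) / 0.1000) = Φ(0.944) = 82.8%

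Exact enumeration gives 81.8%. The stated 82% reproduces. The exact size of this test at a common rate of 45% is 4.6%.

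**2. How often chance produces an imbalance.** For eight independent attributes, the probability of at least one flagged is 1 − 0.95⁸ = 34% at p<0.05 and 1 − 0.90⁸ = 57% at p<0.10. Height, weight and BMI are linked, so the true figures are lower: about 30% and 53% under plausible assumed correlations.

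**3. Continuous outcome.** Assumptions, none from the documents: true difference 0.5 SD; eight independent attributes, two of them prognostic with correlation r to outcome; screening by t-test at 0.05 or 0.10.

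Non-centrality without adjustment is 0.5 × √(45/2) = 2.372, giving power 65%. Fixing the two prognostic attributes divides it by √(1 − 2r²): 2.372/√0.92 = 2.473 for r = 0.2 and 2.372/√0.68 = 2.876 for r = 0.4. Non-central t power is then 69% and 81%. Simulation gives slightly less, because it includes the cost of chance covariate imbalance:

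| Analysis | Power, r = 0.2 | Power, r = 0.4 | Size |
|---|---|---|---|
| Unadjusted | 65% | 65% | 5% |
| Adjusted only if imbalanced | 64% | 65–66% | about 4–5% |
| Two covariates fixed in advance | 67–68% | 80% | 5% |

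Screening matches no adjustment to within about a point. Fixed covariates add 67 − 65 = 2 points at the low end and 80 − 65 = 15 at the high end.

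**4. Stronger covariate, as a sensitivity check.** With one covariate explaining half the variance and a 0.6 SD difference, power is 79.4% unadjusted, 81.4–82.9% screened and 97.8% fixed. Screened size is 3.1–3.5%. The screen recovers at most 82.9 − 79.4 = 3.5 of the available 97.8 − 79.4 = 18.4 points.

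**5. Binary endpoint, 60% against 30%.** One covariate of assumed odds ratio 2 or 3 per SD:

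| Analysis | Power, OR 2 | Power, OR 3 | Size |
|---|---|---|---|
| Unadjusted Z-test | 81.2% | 81.4% | 4.6% |
| Adjusted only if imbalanced | 81.6–81.8% | 82.2–82.9% | 4.0–4.4% |
| Logistic, covariate fixed | 85.4% | 89.0% | 5.1–5.2% |

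Part of the last row's advantage reflects its slightly larger size.

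**6. Free choice.** If the analyst reports the better of the unadjusted and the imbalance-adjusted result (continuous outcome, one or eight attributes), size is about 5.2–5.9%.

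**The case against.** The strongest reply is that the plan commits to no harmful procedure. It says that attributes are assessed. It specifies no test, threshold, covariate selection or adjusted model, and confounding involves association with outcome, which a baseline-only screen ignores. That stands: the screened results describe what would happen if adjustment followed imbalance.

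A reader might infer an inflated false-positive rate. The documents do not support that. Mechanical screening makes the test conservative if anything, and inflation needs a free choice between results, which the plan does not propose (though it does not exclude it) and which is small here. A reader might also infer that the planned power is eroded. It is not: the 82% belongs to an unadjusted test, and screening costs about a point at most against no adjustment. The 2 to 15 points are a gain forgone, of assumed size.

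Two further points have force. By group could mean subtype, since the sentence follows the subtype analysis; but position and the earlier use of groups for the two drugs in 3d favour the drug arms. More importantly, sections 2a and 3b allow early switching for intolerance, the sample size text speaks of subjects using each drug, and no analysis set is defined. If groups were formed by drug taken, imbalance would not be pure chance and a confounding check would be proper. Deleting the phrase is therefore right only once this component is defined by randomised drug.

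**Conclusion.** The point holds as one about method, of modest weight. In the randomised comparison an assessment for confounding has no useful role, and any adjustment it triggered would give a test of about 4 to 5% size with essentially no gain in power. A short covariate set fixed in advance is better: roughly 2 to 15 points for a continuous outcome at 45 per arm and 0.5 SD.

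That range rests on assumed correlations of 0.2 to 0.4 for two covariates. The documents give no prognostic strengths, and with covariates unrelated to outcome the gain is nil. The sample size needs no change, and the sized Z-test gains nothing from the fix because it stays unadjusted. The conclusion also requires groups analysed as randomised, which section 3d does not yet say.

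**What to change.** In section 3d:

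- State that the two-month comparison is analysed by randomised drug, whatever was later taken.
- Keep the baseline table descriptive, and select no covariates from differences seen by arm.
- Keep the unadjusted two-group Z-test as the sized test, and support it with a pre-specified analysis adjusted for subtype.
- For MSQ and DHI, adjust for the pre-randomisation score and subtype whatever the observed balance. The pre-randomisation score then enters as a covariate and not as one of the repeated outcomes.
- Confine confounding assessment to the non-randomised comparisons: diet, patients who change drug, and any as-treated analysis.

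Settle this before outcomes are seen by drug. Subtype, MSQ and DHI are already collected before allocation, so no new data are needed. The cost is two degrees of freedom for subtype and one for the score, about three out of 90 subjects. If neither is prognostic, power at 0.5 SD stays at about 65%.
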